### **Endoscopy**

An endoscopy will be performed on the following visits:

- During Screening\*
- Week 12
- Week 56/Premature Discontinuation if PD occurs after Week 26

It is expected all subjects will have a Week 12 and 56/PD Endoscopy. Site staff should schedule the Week 12 Endoscopy during the Baseline visit, if possible. For subjects that PD, the site should attempt to reschedule the Endoscopy prior to the discontinuation visit.

\*An endoscopy performed before the Screening visit, may be used as the Screening endoscopy, with the approval of the AbbVie Study Designated Physician, if the following conditions are met:

1. biopsy confirmation of the diagnosis is available according to section "Biopsy During Endoscopy" below.
2. the endoscopy took place within 45 days before Baseline Visit.
3. the endoscopy was performed and recorded in a video format as the endoscopic eligibility will be determined by the central reviewers. The same endoscopist, where possible, should perform all endoscopies.

All ileocolonoscopies should be performed and recorded in a video format during the Screening Period or endoscopy performed within 45 days before Baseline and the

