Week 56/PD visit. Sites should also perform an SES-CD assessment and record findings on the provided SES-CD score sheet, refer to [Appendix M](#). The findings should be entered in the appropriate eCRF. Videos from Screening endoscopies from subjects the Investigator believes are eligible for the trial (i.e., subjects with an SES-CD  $\geq 6$ , excluding the presence of narrowing component, (or SES-CD  $\geq 4$ , excluding the presence of narrowing component, for patients with disease limited to the ileum), and all Week 12 and Week 56/PD endoscopies conducted will undergo central review. Two primary central reviewers will evaluate the data and provide their score. If the SES-CD scores are discrepant between the two readers, a third central reviewer will review the video and choose between the first and second reviewers' scores. The third reviewer's choice between the reviewers' scores will be considered final. This process will apply to all video endoscopies where the first and second reviewers do not agree. The adjudicator's assessment will be considered final. If, in the opinion of the Investigator, the Screening endoscopy does not indicate the SES-CD criteria confirming study eligibility, the subject should be screen-failed and the video should not be sent for central review. Endoscopic eligibility will be determined by the central reviewers. The same endoscopist, where possible, should perform all endoscopies.

The endoscopy during the Screening Period or endoscopy performed within 45 days before Baseline and Week 56/PD will be used to provide the endoscopy subscores for calculating the Simplified Endoscopic Score (SES-CD) at Screening, Week 12, and Week 56/PD, refer to [Appendix M](#). The SES-CD values provided by the central reader will be used for all endpoint analyses.

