4.2 Study Design and Design Diagram

This is a randomized, double-blind multicenter study of two adalimumab induction and maintenance regimens in subjects with moderately to severely active CD with evidence of mucosal ulceration confirmed by central reading. No placebo arm is planned since there is well-documented efficacy of adalimumab in CD and because the purpose of this study is to achieve better efficacy than the standard induction and maintenance regimens in terms of clinical remission and endoscopic response. Additionally, since subjects will be required to have failed or been intolerant of standard therapies and have evidence of endoscopic damage confirmed by a central reader, it would be not medically acceptable to deny those subjects effective treatment or feasible to enroll subjects in the trial when adalimumab is available to be prescribed for CD.

Approximately 500 adult subjects with active Crohn's disease, defined as having a CDAI of ≥ 220 and ≤ 450 and evidence of mucosal ulceration defined as SES-CD ≥ 6 , excluding the presence of narrowing component, or SES-CD ≥ 4 , excluding the presence of narrowing component, for patients with disease limited to the ileum on screening endoscopy or endoscopy performed within 45 days before Baseline, confirmed by a centrally read endoscopy, will be enrolled at approximately 150 sites worldwide.

Subjects who meet all of the inclusion criteria and none of the exclusion criteria will be enrolled into the study and randomized in a 3:2 ratio at Baseline to receive a higher

induction adalimumab regimen or standard induction adalimumab regimen during the double-blind Induction Study.

The randomization of subjects for the Induction Study will be stratified by hs-CRP at Baseline (< 10 and ≥ 10 mg/L), using the Screening hs-CRP value, prior infliximab use, and Crohn's disease activity (CDAI ≤ 300 , > 300), at Baseline. Enrollment of subjects with prior infliximab use will be limited to 25% of the total study population.

[figure not shown]

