If a subject met censoring criteria for CD-related concomitant therapy, 'discontinued steroid use' will be classified as No from that point through the end of the study.

SES-CD Scoring

All videotaped colonoscopies will undergo central review providing the investigator's SES-CD score meets the entry criteria. Two primary central reviewers will evaluate the videotaped colonoscopies separately and provide their SES-CD scores to Parexel. A third central reviewer will adjudicate between the two initial reviewers' SES-CD scores if there is discrepancy in any SES-CD variable. The adjudicator will select the final SES-CD score that he/she most agrees with from those provided by the two primary reviewers, and this final SES-CD score will be entered into the study database and be used for the study's efficacy analyses. If there is no discrepancy between the two primary central reviewers, that score will be entered into the study database and serve as the SES-CD score to be used for the study's efficacy analyses.

If there is a missing SES-CD individual variable in the SES-CD that serves as the SES-CD for the study's efficacy analyses, the following imputation rules will be applied:

The missing SES-CD individual variables at Baseline will be imputed as 0. The post-Baseline missing SES-CD individual variables will be imputed as 0 if there are 8 or fewer missing individual variables. If more than 8 individual variables are missing, the total SES-CD will be missing for that visit.

Bristol Stool Chart Score

Up to 14 days of diary entries will be evaluated from the ePRO tool for the Bristol Stool Chart calculation. These assessments on the day of endoscopy procedure, the day before endoscopy procedure (due to preparation medications), and 2 days after endoscopy procedure are excluded. The 7 most recent non-missing assessments will be used for the analysis. Bristol Stool Form Scale is not a continuous variable. The new variable Bristol Stool Chart score is defined as the number of days the subjects with Type 6 or Type 7 divided by the total number days with non-missing assessments, rounded to two decimal.

If a subject has less than 4 days of diary data, the Bristol Stool Chart score will not be calculated and will be considered missing.

If a subject achieved reduction from Baseline $\geq 50\%$, this subject will be classified as Bristol Stool Chart Responder.

Hs-CRP

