10.2 Primary Efficacy Analyses

This section provides the details of the primary efficacy analysis for the Induction Study.

Co-Primary Efficacy Variables:

- Proportion of subjects who achieve clinical remission at Week 4 (CDAI < 150).
- Proportion of subjects with decrease in SES-CD > 50% from Baseline (or for a Baseline SES-CD of 4, at least a 2 point reduction from Baseline) at Week 12.

Analysis Data Set for the Primary Efficacy Analysis:

The primary efficacy analysis will use the ITT analysis data set.

Imputation Method Used for the Primary Efficacy Analysis:

Missing CDAI at Week 4 or SES-CD at Week 12 will be imputed using the non-responder imputation (NRI) approach.

Statistical Method of the Primary Efficacy Analysis:

The comparisons between treatment groups on the two co-primary efficacy variables will be performed using the Cochran-Mantel-Haenszel (CMH) adjusted for hs-CRP at Baseline (< 10 and ≥ 10 mg/L), prior infliximab use (or prior anti-TNF use for subjects randomized under original protocol), and Crohn's disease severity (CDAI ≤ 300 , > 300) at Baseline. A CMH based two-sided 95% confidence interval for the difference between treatment groups will be calculated. Breslow-Day test for homogeneity of odds ratios will be performed as well. An exact CMH test will be used to handle zero cells.

For Week 4 clinical remission (CDAI < 150), LOCF, OC and multiple imputation methods will be used as sensitivity analyses. For Week 12 endoscopic response, OC will be used as sensitivity analysis.

In addition, as sensitivity analyses, the logistic regression including treatment, the randomization stratification factors and additional clinically important factors such as corticosteroid use at Baseline, IMM use at Baseline, Baseline fecal calprotectin, Baseline SES-CD, and Region (US versus ex-US) will also be performed for the co-primary endpoints.

The co-primary endpoints will be tested prior to the ranked secondary endpoints.

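### Both SAPs drop the protocol's Screening-only limit on the site-score condition for central reading; followed as written, low-scoring Week 12 and Week 56 scans would count as failures

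*SAP*

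**What the plan says.** **SAPs.** The SES-CD Scoring paragraph in Section 6.0 of both SAPs opens with the same sentence: "All videotaped colonoscopies will undergo central review providing the investigator's SES-CD score meets the entry criteria". It names no visit. Section 4.2 of each SAP gives the endoscopic entry criterion as "evidence of mucosal ulceration defined as SES-CD ≥ 6 , excluding the presence of narrowing component, or SES-CD ≥ 4 , excluding" narrowing, the lower value applying to disease confined to the ileum. Section 6.0 defines endoscopic response and endoscopic remission by the central reviewer's score.

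For missing scores, Induction SAP Section 10.2 says: "Missing CDAI at Week 4 or SES-CD at Week 12 will be imputed using the non-responder imputation (NRI) approach". Maintenance SAP Section 10.2 treats missing categorical endpoints the same way. Neither SAP uses LOCF for endoscopic endpoints; observed case (OC) is the sensitivity analysis.

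**Protocol.** Section 5.3.1.1 (Endoscopy) has two rules. Before Baseline, the videos sent for central review are "Videos from Screening endoscopies from subjects the Investigator believes are eligible for the trial". After Baseline, "all Week 12 and Week 56/PD endoscopies conducted will undergo central review", with no score condition. It adds: "The SES-CD values provided by the central reader will be used for all endpoint analyses".

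Two other sentences in that section leave Week 12 out of a list of scans:
- The recording sentence begins "All ileocolonoscopies should be performed and recorded in a video format during the Screening Period" and goes on to name an acceptable earlier endoscopy and the Week 56/PD visit.
- The sentence on which scans supply the score names the pre-Baseline endoscopy and then reads "Baseline and Week 56/PD will be used to provide the endoscopy subscores for calculating the Simplified Endoscopic Score". It does go on to list Week 12 among the visits for which a score is calculated.

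**Declared differences.** Induction SAP Section 12.1 reports no differences from the protocol. Maintenance SAP Section 12.1 lists some, none of them about central review.

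**The concern.** At Screening the condition is sensible: there is no reason to read centrally a scan that the site already considers ineligible. After Baseline the same condition selects on the outcome. The better the mucosa looks to the site, the less likely the scan is to be read. Since endpoints use only the central score, an unread scan is a missing SES-CD, and non-responder imputation (NRI) turns it into a failure.

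The results exposed are:
- the Week 12 endoscopic co-primary;
- ranked secondary endpoints 2, 5, 9 and 10 of the Induction Study;
- every Week 56 endoscopic endpoint;
- in the Maintenance analysis, the adjustment factor based on the central Week 12 reading, and the denominators restricted to Week 12 endoscopic responders or remitters.

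The two protocol sentences matter for the same reason. Central reading works from video, and Week 12 is the co-primary visit.

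**Working it through.** **1. The rules side by side**

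| Visit | Protocol 5.3.1.1 | Both SAPs, 6.0 |
|---|---|---|
| Screening | Central review if the investigator believes the subject eligible | Central review if the site score meets the entry criteria |
| Week 12, Week 56/PD | Central review of all scans | Same condition as Screening, as worded |

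The documents agree at Screening and conflict after it.

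**2. The plan's own figure.** Inputs from Induction SAP Section 4.3 and Protocol Section 8.2: 300 v 200 subjects, response 66% v 44% (44% × 1.5 = 66%), Fisher's exact test, two-sided 0.05, stated power about 99%. Exact power is the sum, over all pairs (x, y) whose two-sided Fisher p-value is at most 0.05, of Bin(x; 300, 0.66) × Bin(y; 200, 0.44). The result is 99.8%, so the stated figure is reproduced.

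**3. Who would fail the condition after Baseline.** Assume that site and central scores are equal and that there is no narrowing. Let B be the Baseline SES-CD.

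- *Threshold 6.* A responder whose Week 12 scan still qualifies scores at least 6 with (B − 6)/B > 0.5, so B > 12, that is B ≥ 13. At B = 12 the highest responder score is 5. Every responder with Baseline 6 to 12 fails the condition. At B = 13 or 14 only a score of exactly 6 passes; at B = 20 scores of 6 to 9 pass.
- *Threshold 4 (ileum only).* (B − 4)/B > 0.5 gives B > 8. Every responder with Baseline 4 to 8 fails. One segment with three variables scored 0 to 3 has a maximum of 9, so without narrowing the only responder who passes has Baseline 9 and Week 12 score 4.
- *Remission, SES-CD ≤ 2 and SES-CD = 0.* With threshold 6, a score of 4 or less never qualifies. In ileum-only disease, remission allows no subscore above 1, so the three variables other than narrowing total at most 3, below the threshold of 4. Scores of 2 or less fail under both thresholds. All three endpoints would be unattainable.

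**4. Illustration for the co-primary.** Let f be the share of true responders left unread. The documents give no Baseline SES-CD distribution, so f is an assumption, shown over a range and taken as equal in both arms. Observed rates are 0.66 × (1 − f) and 0.44 × (1 − f).

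| f | Higher | Standard | Difference (points) | Fisher power |
|---|---|---|---|---|
| 0 | 66.0% | 44.0% | 22.0 | 99.8% |
| 25% | 49.5% | 33.0% | 16.5 | 95% |
| 50% | 33.0% | 22.0% | 11.0 | 76% |
| 75% | 16.5% | 11.0% | 5.5 | 38% |

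If the higher regimen healed more deeply, f would be larger in that arm. At an assumed 75% v 60% the rates are 0.66 × 0.25 = 16.5% and 0.44 × 0.40 = 17.6%, and the difference reverses.

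**5. The sensitivity analysis.** OC omits subjects without a score. It would omit the same unread scans and could not recover the lost responders.

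**6. After correction.** With all Week 12 scans read, f = 0, and the planned rates and power are unchanged.

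**The case against.** The strongest reply is that the protocol governs and already has the right rule. The SAPs say that they elaborate the protocol's methods; they guide programming and do not tell sites which videos to submit. Their own content also contradicts the literal reading:
- They plan endoscopic remission, SES-CD ≤ 2 and SES-CD = 0 as endpoints, which would be empty.
- They impute missing post-Baseline SES-CD components.
- The Maintenance models adjust for SES-CD decrease on the central Week 12 reading.
- Induction SAP Section 12.2 explains that the Week 12 window was widened so that collected endoscopies are used.

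A statement of no differences from the protocol likewise suggests that none was intended. On the protocol side, the second sentence does provide for a Week 12 score, and mandatory central review from video implies that Week 12 is recorded.

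Most of this stands, and it is why the sentence looks like a slip. It does not remove the conflict. The sentence opens the paragraph that fixes which score enters the efficacy analyses, that paragraph goes on to post-Baseline rules, and the current Induction SAP revised the paragraph without limiting the condition.

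A reader might infer that most true responders will be imputed as failures, or that most of the 22-point difference would disappear. The documents do not support either statement. Both need a Baseline SES-CD distribution that is not given, and both assume that a filter operates after Baseline, against the protocol's explicit rule. The central-reading instructions, which would settle this, are not among the documents.

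**Conclusion.** The point holds as a conflict between the SAPs and the protocol on a rule that feeds a co-primary endpoint. It is probably a Screening condition written without its visit limit, not a deliberate analysis choice, and nothing shows that any Week 12 or Week 56 scan will go unread.

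Its size is conditional on the sentence being followed. With equal site and central scores, no narrowing and threshold 6, all responders with Baseline 6 to 12 would be lost, and the three strictest endoscopic endpoints could not be met. The effect on power depends on an unknown share of responders lost; the 95%, 76% and 38% figures illustrate losses of 25%, 50% and 75%, equal in both arms. The omission of Week 12 from the two protocol lists is real but lesser, since the surrounding text makes the intention fairly clear. All of this should be put right before database lock.

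**What to change.** 1. In Section 6.0 of both SAPs, replace the sentence with: *Screening colonoscopies are centrally read if the investigator's SES-CD meets the entry criteria; all Week 12 and Week 56/PD colonoscopies are centrally read regardless of the investigator's score.*
2. In Protocol Section 5.3.1.1 (Endoscopy), add Week 12 to the video-recording sentence and to the list of scans that supply the SES-CD subscores.
3. Before lock, check that the central-reading instructions contain no post-Baseline score filter.

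The cost is one sentence in each SAP, two insertions in the protocol and one document check. No reading is added beyond what the protocol already requires, and no planned figure changes.

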7.1 Demographic and Baseline Characteristics

For the subjects in ITT and safety analysis set, demographic information and Baseline values will be summarized by descriptive statistics. Categorical data will be summarized by number and percent; and quantitative data will be presented by n, mean, standard deviation, minimum value, median, and maximum value.

In general, continuous variables will be analyzed using analysis of variance (using SAS procedure 'PROC GLM') with treatment group as factor. Categorical variable will be analyzed using chi-square test or Fisher's exact test if $\geq 20\%$ of the cells have expected cell count < 5 .

The following demographic and Baseline values will be summarized.

Continuous Variables:

- Age (years)
- Body weight (kg)
- Height (cm)
- Body Mass Index (kg/m^2)
- Blood Pressure (systolic/diastolic) (mmHg)
- Pulse (bpm)
- Respiratory Rate (RPM)
- Temperature ($^{\circ}\text{C}$)
- IBDQ score
- CDAI
- SFPS
- Total SES-CD score

- Crohn's Disease Duration (years)
- hs-CRP mg/L
- WPAI and its components
- EQ-5D
- Abdominal Pain Rating Scale
- Bristol Stool Chart score
- Fecal calprotectin

Categorical Variables:

- Sex (male, female)
- Race
- Ethnicity
- Age (\leq median, $>$ median)
- Age (< 40 , 40 to < 65 , 65 to < 75 , ≥ 75)
- Baseline fecal calprotectin (\leq median, $>$ median)
- Baseline corticosteroid use (yes, no)
- Baseline immunosuppressant use (yes, no)
- hs-CRP at Baseline (< 10 and ≥ 10 mg/L)
- hs-CRP at Baseline (\leq median, $>$ median)
- Baseline fecal calprotectin (\leq median, $>$ median)
- Baseline fecal calprotectin (≤ 250 $\mu\text{g/g}$, > 250 $\mu\text{g/g}$)
- Crohn's disease severity (CDAI ≤ 300 , > 300) at Baseline
- Baseline CDAI (\leq median, $>$ median)
- Baseline SES-CD (\leq median, $>$ median)
- Prior infliximab use (or prior anti-TNF use for subjects randomized under original protocol) (yes, no)
- Weight (\leq median, $>$ median)
- Baseline albumin (\leq median, $>$ median)
- Disease duration (\leq median, $>$ median)

- Disease duration (≤ 3 years, > 3 years)
- Tobacco use (user, ex-user, never used, unknown)
- Alcohol use (drinker, ex-drinker, non-drinker, unknown)
- Region (US, ex-US)

7.2 Medical History

Medical and Surgical History: A complete medical and surgical history (which includes CD-onset date), history of tobacco and alcohol use, will be obtained from each subject during the Screening period. Medical history will be summarized using body system and preferred term by treatment group. No statistical tests will be performed.

Chest X-Ray Results: All subjects undergo a standard chest X-ray of chest (including a posteroanterior [PA] and lateral view) at Screening period. Number and percent of subjects with presence or absence of finding for the previous TB infection, calcified granulomas, Pleural scarring/thickening, and other findings will be presented by treatment group. No statistical tests will be performed.

TB Test Results: Results of PPD skin test or QuantiFERON-TB Gold test at screening visit will be summarized. Induration will be summarized descriptively using n, mean, standard deviation, minimum values, median, and maximum values. The frequency distribution of induration ≥ 5 and < 5 will be provided. No statistical tests will be performed.

ECG Results: ECG results at screening will be presented as frequency distribution showing results as Normal, Abnormal (Not clinically significant), Abnormal (Clinically significant) and Unable to evaluate/missing. No statistical tests will be performed.

7.3 Previous Treatment and Concomitant Medications

Prior medications are those medications taken prior to the first dose of study drug. This includes medications with a start date before the first study drug administration date,

regardless of the end date of these medications. Medications taken on the day of the first dose of study drug are not counted as prior medications.

Concomitant medications are those medications, other than study drug, taken after the first dose of study drug. For this interim analysis, concomitant medications include medications with a start date prior to the Baseline date which are continuing after Baseline and all medications with a start date between the Baseline date and last study drug administration + 14 days or until first dose of maintenance study drug/Study M14-347 study drug, whichever is earlier.

Based on generic medication names, these categories of medications used by subjects before and during the study will be summarized by number and percent for ITT and safety analysis sets for the treatment groups. No statistical tests will be performed.

The number and percent of subjects using Crohn's disease specific medications (including corticosteroids [$0, \leq 10$ mg, ≤ 20 mg, or ≤ 30 mg prednisone equivalents], aminosalicylates, immunosuppressants, and antibiotics at the Baseline will be tabulated. In addition, the number and percent of subjects using any Crohn's disease specific medications including infliximab prior to Baseline will be tabulated.

8.0 Patient Disposition

Subject disposition will be presented for subjects in the ITT and safety analysis sets using the following information by treatment group:

- Number and percent of subjects in various analysis sets by treatment group and by investigator and/or site number
- Number and percent of subjects completing 12-week Induction study
- Subject disposition including the number and percent of subjects who prematurely discontinued the Induction study (on or before Week 12) by primary reason and by any reason

Summary of protocol deviations will be provided.

